6.3 Notification of deaths

All deaths where there may be a relationship between the trial interventions or the condition being studied will be reported by the CI to the sponsor. This report will be as soon as the CI becomes aware of the event. Reporting processes to other organisations (REC and the manufacturer) will be as documented above.

6.4 Reporting urgent safety measures

If any urgent safety measures are taken the CI/Sponsor shall immediately and in any event no later than three days from the date the measures are taken, give written notice to the relevant REC of the measures taken and the circumstances giving rise to those measures.

6.5 Assessment and management of risk

Carbon fibre shoe inserts are currently used in the NHS.

BigTOE Trial Protocol

A risk assessment for the trial will be performed according to Warwick Standard Operating Procedures (SOP) and a monitoring plan developed depending on the risks identified. Risks specific to the trial include risks of data breaches, incorrect allocation, or failure to recognise safety concerns. These risks will all be carefully managed by following University of Warwick SOPs and careful adherence to the principles of Good Clinical Practice (GCP).

7. Data management

Personal data collected during the trial will be handled and stored in accordance with the 2018 Data Protection Act and UK GDPR. Confidential data will be handled in line with the Common Law Duty of Confidentiality.

Personal identifying information will be collected via the online database and stored electronically at WCTU. Participant details will be entered by staff at sites or WCTU, and will be stored and accessed via staff at WCTU to confirm eligibility and consent; allow postage of participant questionnaires; contact participants during the trial; and contact for qualitative interviews. Handling of personal and confidential data will be clearly documented in the participant information sheet and consent obtained.

Data containing of personal identifying information (participant contact details or consent forms) will be stored separately from the remaining trial data to safeguard it

Disclosure of confidential information will only be considered if there is an issue which may jeopardise the safety of the participant or another person, according to Warwick Standard Operating Procedures (SOP 15 part 1) and the UK regulatory framework. There is no reason to expect this situation to occur in this trial more than any other.

7.3 Data collection and management

The CRFs will be developed by the TM in consultation with CI, Trial Statistician, Health Economist and other relevant members of the trial team to collect all required trial data. In the first instance documents will be produced in English and other languages will be considered after the pilot phase.

All data will be entered directly either by participants, by site staff or by WCTU trial team members onto a secure online database hosted by WCTU as outlined in the data management plan and accordance with the Warwick SOPs.

Data entered onto the online study database by site staff or participants will be source data. This will be stored on Warwick secure servers. CRF entries will be considered source data if the CRF is the site of the original recording (e.g. there is no other written or electronic record of data). All documents will be stored safely in confidential conditions. On all trial-specific documents, other than the signed consent, the participant will be referred to by the trial participant number/code, not by name.

Various methods will be used to chase missing data including phone, text and email. Participants will receive a reminder to complete the online questionnaires at each study time point. Participants will also be offered paper-based questionnaires for completion if preferable. If a participant has not completed a study questionnaire following the reminder, the BigTOE trial team will contact the participant to encourage them to complete the questionnaire online, and to provide support where required. If data remains missing following this chase, the BigTOE trial team will contact the participant to attempt to collect the outcome measurements with priority on the core measures (MOXFQ and EQ5D-5L). Missing data at a timepoint will not preclude collection of data at subsequent

follow-up timepoints. The procedures for managing this will be outlined in the data management plan and appropriate consent will be sought to contact participants.

Data will still be collected for participants who discontinue or deviate from the intervention, unless they withdraw their consent (Section 3.9.1). Data that can identify participants by name and their contact details will be deleted once all analysis and participant dissemination is complete.

7.4 Database

The database will be developed by the Programming Team at WCTU and all specifications (i.e. database variables, validation checks, screens) will be agreed between the programmer and appropriate trial staff.

7.5 Data storage

All essential documentation and trial records will be stored at Warwick Clinical Trials Unit in conformance with the applicable regulatory requirements and access to stored information (paper and electronic) will be restricted to authorised personnel. All paper data will be stored in a designated ar facility within the WCTU (a restricted access building). Electronic data will be stored on password protected university computers in a restricted access building. Guidelines for data management will be outlined in the trial data management plan.

7.6 Data access and quality assurance

Most data will be received directly from participants who will enter their data into the online study database. After the collection of the baseline demographic data for each participant and following randomisation all data will be pseudonymised. Confidentiality will be strictly maintained and names, addresses or personal identifiable information will not be disclosed to anyone other than the staff involved in running the study. All electronic participant-identifiable information will be held on a secure, password-protected database accessible only to essential personnel. Paper forms will be held in secure, locked filing cabinets within a restricted area of WCTU. Participants will be identified by a participant number only on the paper forms. Any identifiable participant hard copy data will be held separately in a locked filing cabinet and coded with the trial number to tag identifiable data to the outcome data.

Direct access to source data (online study database) will be available for study-related monitoring or audit by WCTU for internal audit or regulatory authorities. The PI must arrange for retention of study records on site in accordance with GCP and local Trust's policies.

Direct access to source data/documents will be required for study-related monitoring. For quality assurance, the data and results will be statistically checked. A full data management plan will be produced by the study Trial Manager and Statistician to outline the data monitoring checks required.

7.7 Data Shared with Third Parties

Requests for data sharing will be managed in accordance with Warwick Clinical Trials Unit SOP 15 Part 3. The datasets generated during and/or analysed during the current study are/will be available upon request after publication of the main study results. The publication of a study protocol, study results and study data will comply with the NIHR standard terms and will follow Warwick SOP 22: Publication & Dissemination.

7.8 Archiving

Trial documentation (including the ISF) and data will be archived for at least five years after completion of the trial.

8. Statistical Analysis

8.3 Power and sample size

The MOxFQ is a 16-item questionnaire with three subdomains to assess standing/walking problems, pain and social interaction in people with foot and ankle problems. It was co-selected with our PPI partners. This scale is well accepted by patients with a range of foot conditions, including painful OA.[26, 39] We will use the Walking/Standing subdomain as our primary outcome, which comprises of seven items.

The standard deviation (SD) of the MOxFQ standing/walking subscale in a previous study of 1st MTPJ pathology was 23 points.[39] To our knowledge, there are no data on a worthwhile difference for conservative interventions for 1st MTPJ OA. However, Dawson *et al.* found that for people undergoing surgery for hallux valgus, the minimum clinically important difference was 16 points for the standing/walking subdomain. As this trial will assess a cheaper, non-surgical intervention, we have set a smaller value to be worthwhile. We have conservatively set the target difference to 8 points on the MOxFQ standing/walking subscale. This corresponds to an improvement in just over two item categories such as: a change from 'All of the time' to 'Some of the time' in one item, or a change from 'Most of the time' to 'Some of the time' in two items. Our patient partners agree that this modest change would be a worthwhile difference, particularly given the lack of other evidence-based treatment options for this condition. This also corresponds to a standardised effect size of 0.35, which is similar to other conservative intervention trials for musculoskeletal conditions (e.g. AIR[40], ARTISAN[41]).

Hence, to show a between group difference of 8 points on the standing/walking sub-score of the MOxFQ, assuming that the SD at three months post randomisation is 23 points, at 90% power and 5% significance, data are needed on 350 participants. Allowing for 20% loss to follow up, whilst aiming to keep this below 10%, 438 participants are required.

Table 4: Considered sample sizes

Between group difference in MOXFQ at 3 months	Effect size	n per group	N per group with 20% ltfu*	Total N (20% ltfu*)
7	0.30	228	285	570
8	0.35	175	219	438
9	0.39	139	173	346

*Itfu = loss to follow-up

8.3.1 Sample size re-estimation

As a robust estimation of the SD of the MOXFQ in this population is unknown, we will conduct a blinded sample size re-estimation to further inform study power. A blinded method will be used as this will not affect the type I error rate. At the end of the internal pilot, when approximately 50 participants have reported their primary outcome measure, the observed SD will be calculated from the blinded (pooled) data and used to re-estimate the sample size. The results will be presented to the oversight committees and the target sample, and if necessary, the sample reduced. An increase is not anticipated, as only large increases, such as 33% are considered worthwhile.[42]

8.4 Statistical analysis of efficacy and harms

8.4.1 Planned recruitment rate

We anticipate a recruitment rate of 1 participant per site per month. With a staggered opening of sites, we anticipate it will take 18 months across approximately 25 sites to complete recruitment.

8.4.2 Internal pilot study and progression criteria

The first nine months of randomisation will act as an internal pilot, with a green target of n=111 randomised, based on staggered opening of sites. We will apply stop-go rules with the same percentage thresholds as used for other recent musculoskeletal trials in our unit (e.g. ARTISAN and RACER (NIHR HTA 13/84/10 & 128768). We will collect follow up data for an additional month to ensure that sufficient data on the primary outcome are collected to inform sample size re-estimation.

If the study meets amber criteria, we will inform the TSC, review all trial processes, open additional sites or adapt trial processes, and review these again within three to six months. If the red criteria are met, we will consider stopping the trial after discussion with the TSC and funder.

Table 5: Feasibility criteria

	Red	Amber	Green
% Threshold	< 66%	66% to 99%	≥ 100%
Recruitment rate of sites per month	< 1	1 – 2	≥ 2
Number of sites opened	< 6	7 – 8	≥9
Total number of participants recruited	<73	73 – 110	≥ 111
Primary outcome data received	<36	36 – 54	≥ 55

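### Table 5 gives no colour to six open pilot sites and two colours to a rate of exactly 2, and its rate limit of 1 is 50% of the green value

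*Protocol*

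**What the plan says.** Protocol section 8.4.2 treats the opening nine months of recruitment as the pilot and states its goal as follows: "with a green target of n=111 randomised, based on staggered opening of sites". On the decision rule it says: "We will apply stop-go rules with the same percentage thresholds as used for other recent musculoskeletal trials in our unit". Those percentages form the first row of Table 5: "Threshold < 66% 66% to 99% ≥ 100" (the last figure is also a percentage).

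Four criteria are then banded into red, amber and green:

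- Sites, the row with the gap: "Number of sites opened < 6 7 – 8 ≥9".
- Rate, the row with the overlap, printed above it: "Recruitment rate of sites per month < 1 1 – 2 ≥ 2".
- Participants: red is under 73, amber runs from 73 to 110, and green begins at 111.
- Outcome data: red is under 36, amber runs from 36 to 54, and green begins at 55.

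The colours carry different actions. For amber: "If the study meets amber criteria, we will inform the TSC, review all trial processes". More sites or adapted processes would then follow, with a second look three to six months later. For red, the team would discuss with the TSC and the funder whether to stop. The section does not say how six sites or a rate of exactly 2 is to be classed.

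**The concern.** Progression criteria are useful because every possible pilot result has one colour before the result is known. Two of the four rows in Table 5 fail that test at a boundary. The sites row skips a value, and the rate row assigns one value twice. The rate row also places its red/amber boundary well below the percentage that heads the table.

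At stake is which of the stated actions follows. Six sites lies on the boundary between reviewing the trial and considering whether to stop it. A rate of 2 lies between carrying on and reviewing. Rates between 1 and 1.32 are amber by the printed cell and red by the percentage row. In each case someone would have to choose the reading once the pilot figures were in.

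**Working it through.** **Inputs (all from Protocol section 8.4.2, Table 5).** Percentage rule: red below 66%, amber from 66%, green from 100%. Green values: rate 2, sites 9, participants 111, primary outcome data 55. The amber column is headed up to 99%. I read this as anything short of 100%, because the participant row prints 110 as amber and 110/111 = 99.1%.

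**Step 1: reproduce the printed lower limits.** Formula: limit = 0.66 × green value.

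| Row | 0.66 × green | Rounded to nearest | Red is below | Amber starts at | Amber start as % of green |
|---|---|---|---|---|---|
| Rate | 0.66 × 2 = 1.32 | 1 | 1 | 1 | 1/2 = 50% |
| Sites | 0.66 × 9 = 5.94 | 6 | 6 | 7 | 7/9 = 77.8% |
| Participants | 0.66 × 111 = 73.26 | 73 | 73 | 73 | 73/111 = 65.8% |
| Outcome data | 0.66 × 55 = 36.3 | 36 | 36 | 36 | 36/55 = 65.5% |

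All four red limits equal 66% of the green value rounded to the nearest whole number. The one printed edge that this rounding does not reproduce is the start of amber for sites, which is 7 where 6 is expected.

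**Step 2: test each row for gaps and overlaps.**

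- Sites: 6 is not below 6, not 7 or 8, and not 9 or more, so it has no band. By the percentage row, 6/9 = 66.7%, which is amber. Every other whole number falls in exactly one band.
- Rate: 2 satisfies both amber (1 to 2) and green (2 or more). By the percentage row, 2/2 = 100%, which is green.
- Participants and outcome data: every whole number falls in exactly one band, with amber stopping one short of green (110 against 111, 54 against 55).

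**Step 3: size of the rounding in the rate row.** For participants, rounding moves the limit from 66% to 65.8% of target, and for outcome data from 66% to 65.5%. For the rate, rounding 1.32 to 1 moves it from 66% to 50%. A rate of 1.00 is 50% of target and 1.31 is 65.5%. Both are printed amber, and both are below 66% and therefore red by the percentage row.

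**Step 4: what the rate row measures.** Its label can be read as participants recruited per site per month or as sites recruited per month. The overlap at 2 and the 50% limit hold on either reading. A limit of 1.32 makes sense only for a continuous rate. If the row means participants per site, the rate of 1 per site per month anticipated in section 8.4.1 sits exactly on the printed lower amber limit, so the choice between 1 and 1.32 decides how that rate is coloured.

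**The case against.** The strongest reply is that the percentage row governs and the cells are slips against it. The text says that the rules are percentage thresholds, and the first row states them. On that reading six sites is amber and a rate of 2 is green, with nothing left open. This largely stands: the row shows what was intended in both boundary cases. It does not remove the defect, because the document does not say that the percentage row overrides the printed cells, and in the rate row the two give different answers over a whole range.

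A reader might infer that the table disregards its own 66% rule. The figures do not support that. All four red limits are 66% rounded to a whole number, and in the participant and outcome rows the difference is trivial. The rate row is the same rounding applied to a target of 2, where it is too coarse to keep the percentage.

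The reply can also fairly say that red leads only to a discussion about stopping, that the rate overlap lies away from the stopping boundary, and that nothing shows six sites or a rate of exactly 2 to be likely. These points limit the importance of the defect. They do not make the bands correct.

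**Conclusion.** The point holds in a limited form. Table 5 leaves six sites without a colour and gives a rate of exactly 2 two colours. The rate row's lower limit of 1 is 50% of its green value where the table's percentage is 66%, so rates from 1.00 to 1.31 are amber by the cell and red by the percentage row. The first two faults are plain on the face of the table. The third rests on taking the percentage row as the rule for every criterion, which is how the text presents it, and it has practical meaning only if the rate is continuous.

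A reader might go further and infer that the pilot decision is left wholly open, that the planned recruitment rate is wrong, or that the worst row should set the overall colour. The first goes too far, because the percentage row indicates the intended class in both boundary cases. The second is not shown by anything in Table 5. The third would be a new decision rule, and none of these faults calls for it.

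The effect is confined to the feasibility stop-go decision. These criteria are counts and rates, not treatment comparisons, so type I error, the sample size of 438 and the primary analysis are untouched. The table should still be corrected, since its colours trigger different stated actions.

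**What to change.** Amend Table 5 before the pilot review:

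- **Sites opened:** red below 6, amber 6 to 8, green 9 or more.
- **Recruitment rate:** make the bands non-overlapping, with amber ending below 2 and green at 2 or more.
- **Rate label:** state what the row measures and in what unit. If it is a continuous rate of participants per site per month, either set the red/amber limit at 1.32 (66% of 2) or keep 1 and state that a 50% limit is intended for this row.

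The participant and outcome rows can stay, since they differ from 66% only by rounding. The cost is a correction to two rows of one table and one clarifying phrase. No data collection, sample size or analysis changes.

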8.4.3 Statistical analysis plan

A full and detailed Statistical Analysis Plan (SAP) will be developed and agreed with the DMC prior to the primary analysis taking place. Exact details of the sample size estimation procedure will be agreed *a priori* and rules to change the planned sample size agreed prior to the estimation analysis point. Treatment effects will be presented with appropriate 95% confidence intervals. Tests will be two-sided and considered to provide evidence for a significant difference if p-values are less than 0.05 (5% significance level).

Analyses will be conducted as intention to treat basis unless otherwise specified, with exact details of the estimates given in the SAP.

Analyses will predominately carried out using R (www.r-project.org).

8.4.4 Summary of baseline data and flow of patients

Descriptive statistics of baseline and all follow up outcomes will be constructed, dependent on distribution (e.g. means and standard deviations for continuous data). Baseline data will be summarised to check compatibility between treatment arms. Screening data will also be summarised to highlight any characteristic differences between those individuals in the study, those ineligible, and those eligible but withholding consent for the study.

A CONSORT flow diagram will be produced and will be regularly updated for TMGs, TSCs and DMCs at the study progresses (http://www.consort-statement.org)

8.4.5 Primary outcome analysis

The primary analysis will be a conducted on an intention to treat basis, using a generalised linear model containing allocation group, recruitment site, baseline function and bilateral/unilaterality, along with any variables found to be meaningfully unbalanced at baseline by chance.

8.4.6 Secondary outcome analysis

Standard statistical summaries (e.g., medians and ranges or means and variances, dependent on the distribution of the outcome) will be presented for the primary outcome measure and all secondary outcome measures. Secondary outcomes will be modelled similarly to the primary outcome, dependent on distribution. Sensitivity analyses will be used to explore modelling assumptions, with both fixed and random effect models used.

Sensitivity analyses to explore the effects of nonadherence or treatment switching may also be conducted to aid inference. We will use per protocol or complier average causal effect analyses (CACE), as appropriate and note that these were the two most common approaches used in our recently published systematic review of adherence in NIHR funded trials.[36]

Missing data will be scrutinised and where possible, reasons for missingness collected. If judged necessary, missing data will be modelled using multiple imputation techniques as a sensitivity analysis.

We will conduct a subgroup analysis to investigate the impact of the Zammit clinical criteria[28], which are specific to the 1st MTPJ, versus NICE criteria for the diagnosis of OA[27], which are not joint-specific. This analysis will follow the primary analysis methods, with an additional interaction term incorporated into the mixed-effects regression model.

9. Health economic evaluation

A detailed health economic analysis plan (HEAP) in concordance with the SAP will be developed. The economic evaluation will aim to assess the cost-utility of carbon fibre shoe-stiffening inserts compared with sham inserts for the management of 1st MTPJ OA in the UK NHS setting. The analysis will be carried out from the perspective of the NHS and personal social services (PSS)[43]. The evaluation will be designed, conducted, and reported following best-practice guidelines conforming to the Consolidated Health Economics Evaluation Reporting Standards (CHEERS)[44].

Healthcare resource utilisation data will be collected from baseline to the 12-month follow-up for both groups using CRFs by site staff and by participants using self-report questionnaires during each follow-up assessment. The resource utilisation will aim to capture the key cost drivers associated with 1st MTPJ OA management including the costs of carbon fibre shoe-stiffening inserts, sham inserts, any healthcare visits, hospital admissions and medications. Healthcare resource use will be costed using appropriate cost data from local and national databases in £ sterling to the most relevant price year available at the time of the analysis. Any prices not in that financial year will be reflated to current prices.

To estimate quality-adjusted life years (QALYs), health-related quality of life (HRQoL) will be assessed at baseline, three, six, and 12 months using the EQ-5D-5L instrument. Using the trapezoidal rule, responses will be used to generate QALYs based on the UK value set (scoring algorithm) recommended by NICE at the time of analysis[45].

Descriptive statistics will summarise costs and QALYs by the intervention and comparator groups. The pattern of missing data will be examined and accounted for using suitable methods for multiple imputation. Using a bivariate regression for costs and QALYs, the base-case analysis will be conducted under an intention-to-treat (ITT) approach to calculate the incremental cost-effectiveness ratio (ICER), as the additional cost per QALY gained with carbon fibre shoe-stiffening inserts compared to sham inserts. Non-parametric bootstrapping will generate mean values and 95% confidence intervals (CIs) for costs, QALYs, and the ICER. The results will be presented using the cost-effectiveness planes and cost-effectiveness acceptability curves (CEACs) will be plotted to illustrate the likelihood of carbon fibre shoe-stiffening inserts being cost-effective compared to sham inserts at the typical willingness-to-pay thresholds. Net monetary benefit (NMB) analysis will also be generated, where a positive NMB indicates that the QALYs outweigh the costs. Secondary analyses will include a societal perspective to look at the wider impact on patients and their families. Deterministic and probabilistic sensitivity analyses will be conducted to explore uncertainties surrounding key parameters and

address concerns regarding the generalisability of the study. Subgroup analyses may be conducted to assess the impact of patient characteristics (e.g., age, gender, severity of OA) on the cost-effectiveness of carbon fibre shoe-stiffening inserts compared to sham inserts.

If costs and outcomes do not converge within 12 months, economic modelling will be undertaken to explore costs and benefits over an extended time horizon of using carbon fibre shoe-stiffening inserts and sham insoles. The time horizon and model type are still to be decided. The model will be populated using data from the trial, published literature and expert opinion. Any future costs and benefits will be discounted at 3.5%.

10. Trial organisation and oversight

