3.11 Trial treatments / interventions

The carbon fibre inserts and sham devices are based on those used in the SIMPLE trial[9] and will be manufactured by Medfac Uk Ltd. under the Kinetec brand. The carbon fibre shoe stiffening insert is sandwiched within a combination of materials as this allows blinding of participants.

Intervention: Full-length carbon fibre shoe-stiffening inserts, covered with foam (such as PPT[®]). A full-length 1mm soft textile covering (e.g. Cambrelle[®], Camtex Fabrics Ltd, UK) will make the carbon fibre insert similar in appearance to the sham.

Sham: Sham inserts are designed to appear identical to the intervention but without the carbon fibre which adds the rigidity.

Layer	Sandwich analogy	Sham	Carbon fibre insert
Top cover	Bread	Standard top cover	Standard top cover
		material e.g. Cambrelle	material e.g. Cambrelle
Upper mid layer	Lettuce	3.2mm foam	3.2mm foam
Lower mid layer	Ham	none	1.5mm thick carbon
			fibre
Bottom cover	Bread	Standard top cover	Standard top cover
		material e.g. Cambrelle	material e.g. Cambrelle

Table 1: Composition of interventions

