3.11.1 Number of shoe inserts to provide per participant

Where participants have unilateral symptoms, we will provide one shoe insert for the **symptomatic foot** only. Where participants have bilateral symptoms, they will be provided with a pair of inserts.

Recognising that swapping shoe inserts from one pair of footwear to another is particularly difficult due to the rigidity of carbon fibre, we will provide participants with **two inserts** per affected foot i.e. either two inserts for those with unilateral symptoms, or four inserts (two pairs) for those with bilateral symptoms.

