3.11.3 Justification for selection of shoe stiffening inserts

The SIMPLE trial found that shoe-stiffening inserts, compared to sham inserts, were effective at reducing joint pain at 12 weeks. There was a statistically significant between-group difference in the primary outcome at 12 weeks favouring shoe stiffening inserts (FHSQ pain domain MD 6.66; 95% Cl 0.65, 12.67; p<0.03) and this benefit was maintained at 24 weeks (MD 9.59; 95% Cl 2.00, 17.18). This lost statistical significance by one year, but the magnitude of difference was similar that observed at 12 weeks (FHSQ pain MD 6.97; 95% Cl -0.60, 14.53). This is a clinically relevant difference in pain at one year. Authors also reported a statistically significant difference favouring the stiffening inserts in foot function (FHSQ) at 24 weeks. Additionally, participant perception of global improvement was higher in the shoe-stiffening insert group (61% vs 34%, RR 1.73, 95% Cl 1.05 to 2.88, NNT 4). The incremental cost-effectiveness ratio was AU\$12,980 per quality adjusted life year (QALY) gained, with a 55% probability of the carbon fibre inserts being cost-effective at willingness-to-pay thresholds greater than \$6,500 per QALY gained. A nested biomechanical study confirmed that carbon fibre shoe inserts decreased the magnitude and rate of 1st MTPJ dorsiflexion whilst walking.[18]

Sham inserts for the trial have been designed in line with recommendations to make them as biomechanically inert as possible and have the same foam and textile top and bottom cover as the intervention, thus looking identical.[33, 34] Mechanical testing has shown that sham inserts have a minimal effect on joint kinematics and shoe-stiffening.[18, 34] The Australian SIMPLE trial sub-study confirmed that sham inserts were as biomechanically inert as possible and were acceptable and credible for trial participants.[9, 18]

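### The economic evaluation lists the sham insert as a cost of care, which lowers the incremental cost of the carbon fibre insert by the sham cost per participant

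*Protocol*

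**What the plan says.** Section 9 (Health economic evaluation) sets out to assess the "cost-utility of carbon fibre shoe-stiffening inserts compared with sham inserts" "for the management of 1st MTPJ OA in the UK NHS setting". On perspective it states: "The analysis will be carried out from the perspective of the NHS and personal social services". Resource use is meant to cover the main cost drivers of managing 1st MTPJ OA, "including the costs of carbon fibre shoe-stiffening inserts, sham inserts, any healthcare visits, hospital admissions and medications". The base-case ICER is defined "as the additional cost per QALY gained with carbon fibre shoe-stiffening inserts compared to sham inserts". If costs and outcomes have not converged by 12 months, a longer-horizon model is to compare carbon fibre inserts with sham insoles. A separate health economic analysis plan (HEAP) is promised. Deterministic and probabilistic sensitivity analyses are announced in general terms, and none is said to remove the sham cost.

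On the device itself, Section 3.11 says: "Sham inserts are designed to appear identical to the intervention but without the carbon fibre which adds the rigidity". Section 3.11.3 adds: "Sham inserts for the trial have been designed in line with recommendations to make them as biomechanically inert as possible". Table 1 gives both devices the same covers and the same 3.2 mm foam; only the 1.5 mm carbon fibre layer differs. Section 3.11.1 supplies "either two inserts for those with unilateral symptoms, or four inserts (two pairs) for those with bilateral symptoms", with no distinction by arm. Section 6.5 says that carbon fibre inserts are already in NHS use. Nothing in the protocol says so of the sham.

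**The concern.** An NHS perspective counts what the payer would bear under each option. The sham exists to blind participants, so what it costs is a cost of doing the research. Listing it among the cost drivers of OA management, and then taking the difference between arms, credits the active arm with a saving that adoption would not bring. That the NHS would not buy the sham is an inference, but it fits the protocol's description of a near-inert look-alike.

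Because the two devices share everything except the carbon layer, costing both largely cancels the shared components, although the NHS would pay for the whole insert. The ICER, the NMB and the acceptability curve all inherit this cost term. A small shift may not be negligible: the only earlier economic result the protocol cites (the SIMPLE trial) put the probability of cost-effectiveness at 55%, close to even.

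**Working it through.** The protocol gives no ICER, unit cost or QALY gain for this trial, so there is no figure of its own to reproduce. The check is algebra plus an illustration on assumed values.

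**Inputs from the protocol**
- Cost items and ICER definition: Section 9.
- Inserts per participant: 2 if unilateral, 4 if bilateral (Section 3.11.1).

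**Notation, per participant**
- Cc: cost of carbon fibre inserts. Cs: cost of sham inserts.
- dO: all other incremental cost. dQ: QALY gain over sham.
- L: willingness-to-pay threshold.

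**Step 1. ICER**
- Sham costed: (Cc − Cs + dO)/dQ.
- Sham at zero: (Cc + dO)/dQ.
- Difference: Cs/dQ. For dQ > 0 the sham-costed ICER is lower by this amount.

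**Step 2. Incremental NMB**
- Sham costed: L·dQ − (Cc − Cs + dO).
- Sham at zero: L·dQ − (Cc + dO).
- Difference: Cs, at every L and whatever the sign of dQ.

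**Step 3. What Cs is.** With unit cost s per sham insert and a proportion p of participants with bilateral symptoms, Cs = s × [2(1 − p) + 4p] = s × (2 + 2p). The protocol states neither s nor an expected p.

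**Step 4. Illustration (all values assumed, dO = 0)**
- Cc = GBP 40, Cs = GBP 20, dQ = 0.01: sham costed (40 − 20)/0.01 = GBP 2,000 per QALY; sham at zero 40/0.01 = GBP 4,000 per QALY.
- Range for Cs of GBP 10–40 and dQ of 0.005–0.04: smallest shift 10/0.04 = GBP 250, largest 40/0.005 = GBP 8,000 per QALY.
- If instead s is GBP 10–30, Cs runs from 10 × 2 = GBP 20 to 30 × 4 = GBP 120. The upper end requires every participant to be bilateral, so a trial mean would lie below it at that price.

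**Step 5. Why the net direction against no-insert care stays open.** Let b be any QALY benefit of the sham over no insert. Taking other costs as equal (an assumption), the ICER against no-insert care is Cc/(dQ + b). It equals the sham-costed ICER when b = dQ × Cs/(Cc − Cs). With the Step 4 values, b = 0.01 × 20/(40 − 20) = 0.01, and 40/(0.01 + 0.01) = GBP 2,000, the same as with the sham costed. A larger b would make the sham-costed ICER too high, a smaller b too low. The protocol gives no value for b.

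**The case against.** The strongest reply is that the sentence describes what will be captured, not what enters the base case, and that the HEAP, which is not shown, may set the sham cost to zero. That deserves weight: nobody can say from the protocol what the final analysis will do. But the protocol is not silent. It names the sham among the cost drivers of care and defines the ICER against the sham arm. A HEAP written to match would carry the cost; one that drops it would depart from the text. Sensitivity analysis on unnamed key parameters does not fix the base case.

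The reply on direction succeeds. A reader might infer that the evaluation as a whole always favours the carbon fibre insert. The documents do not support that. Sham-arm QALYs may include placebo benefit from a device that Section 3.11.3 calls credible to participants, which would shrink dQ and push the ICER the other way. Section 2.3 also lists padding, taping, injections and contoured orthoses as conservative care, so the NHS alternative need not be free.

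Three further limits stand. The protocol does not show that the device is the main cost difference between arms; visits, admissions and medications are counted too. It does not say that sham fitting time will be costed separately. And every pound figure above is an assumption.

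**Conclusion.** The point holds for the cost term. Followed as written, Section 9 nets a blinding device off the cost of the active insert: incremental cost falls by Cs, NMB rises by Cs, and the ICER falls by Cs/dQ when dQ is positive. This direction follows from algebra and rests only on two readings: that listed costs enter the comparison, and that the NHS would not buy the sham. The size is unknown; GBP 250–8,000 per QALY reflects the assumed ranges alone, and the absolute cost per participant may be small. Net bias against NHS care without an insert is not established in either direction. This should be corrected in wording before analysis; it does not threaten the clinical comparison.

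**What to change.** In Section 9 and in the HEAP:
- Treat the sham device as a research cost and set it to zero in the base case.
- If insert fitting is costed, treat sham-specific fitting in the same way.
- Cost the carbon fibre insert in full.
- Report the version with sham costs included as a named scenario analysis.
- Apply the same rule to any extended-horizon model.
- State as a limitation that the QALY difference still comes from the comparison with sham, so costs and effects do not refer to exactly the same alternative.

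The change costs a revision of wording and no new data; sham costs can still be recorded for the scenario. The downside is that the reported ICER becomes slightly less favourable to the insert.
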